9.6	Specimen Banking.....	31
10.0	STATISTICAL CONSIDERATIONS	31
10.1	Study Design/Study Endpoints	31
10.2	Sample Size and Accrual	31
10.3	Data Analyses Plans.....	31

11.0 STUDY MANAGEMENT.....	31
11.1 Institutional Review Board (IRB) Approval and Consent.....	31
11.2 Amendments.....	32
11.3 Registration Procedures	32
11.4 Data Submission.....	32
11.5 Data Management and Monitoring/Auditing	32
11.6 Adherence to the Protocol	33
11.7 Investigator Obligations	33
REFERENCES.....	40

[figure not shown]
LIST OF ABBREVIATIONS

AE	Adverse Event
AED	Antiepileptic Drug
ALT	Alanine Aminotransferase
ALC	Absolute Lymphocyte Count
API	Active Pharmaceutical Ingredient
AST	Aspartate Aminotransferase
BBB	Blood Brain Barrier
BTB	Blood Tumor Barrier
BUN	Blood Urea Nitrogen
CBC	Complete Blood Count
CMP	Comprehensive Metabolic Panel
CR	Complete Response
CT	Computed Tomography
CTCAE	Common Terminology Criteria for Adverse Events
DSMB	Data and Safety Monitoring Board
GLP	Good Laboratory Practices
ECOG	Eastern Cooperative Oncology Group
EIAED	Enzyme-inducing Antiepileptic Drug
HED	Human equivalent dose
H&PE	History & Physical Exam
ICP-MS	Inductively Coupled Plasma Mass Spectrometry
IHC	Immunohistochemistry
IV (or iv)	Intravenously
MTD	Maximum Tolerated Dose
NCI	National Cancer Institute
NOAEL	No-observed-adverse-effect level
ORR	Overall Response Rate or Objective Response Rate
OS	Overall Survival
PBMCs	Peripheral Blood Mononuclear Cells
PD	Progressive Disease
PFS	Progression Free Survival
PO (or p.o.)	Per os/by mouth/orally
PR	Partial Response
RANO	Response Assessment in Neuro-Oncology
REMBRANDT	Repository of Molecular Brain Neoplasia Data
RT-qPCR	Quantitative Reverse Transcription Polymerase Chain Reaction
SAE	Serious Adverse Event
SD	Stable Disease
SGOT	Serum Glutamic Oxaloacetic Transaminase
SPGT	Serum Glutamic Pyruvic Transaminase
SNA	Spherical Nucleic Acid
TUNEL	Terminal deoxynucleotidyl transferase dUTP nick end labeling

NU Study Number: NU 16C01

ULN	Upper Limit of Normal
V _{ss}	Volume of distribution at steady state
WBC	White Blood Cells

STUDY SCHEMA

STUDY SUMMARY

Title	A Phase 0 first-in-human study using NU-0129: a spherical nucleic acid (SNA) gold nanoparticle targeting BCL2L12 in recurrent glioblastoma multiforme or GS patients
Version	December 19, 2018 (Amendment 5)
Study Design	This is a single-arm, open-label, phase 0 first-in-human trial to determine the safety of NU-0129.
Study Center(s)	Northwestern University
Objectives	
Primary Objective:
 
 • To evaluate the safety of NU-0129 SNA gold nanoparticle infusion in patients with recurrent GBM or GS 
Secondary Objectives:
 
 • To evaluate the bio-distribution of NU-0129 in tumor tissue • To evaluate the pharmacokinetics of NU-0129 in blood samples collected at 1, 3, 5, 10, 30, 60 minutes and 4, 8, and 24 hours post-dose • To evaluate the feasibility of NU-0129 administration 
Exploratory Objectives
 
 • To evaluate the Bcl2L12 expression levels and apoptotic markers in the tumor tissue post-treatment • To evaluate preliminary response (Overall Survival and Progression Free Survival at 2 years, as well as Overall Response Rate)
Sample Size	6-8 patients will be enrolled
Diagnosis & Key Eligibility Criteria	
 • Patients should have a diagnosis of recurrent glioblastoma multiforme (GBM) or gliosarcoma (GS) after failing prior therapy. • Eligible patients must be surgical candidates where surgery is felt to be an appropriate treatment option. • Bone marrow and organ function must be adequate as defined below 
 • WBC \geq 3,000/μL • ANC \geq 1,500/mm³ • Platelet count of \geq 100,000/mm³ • Hemoglobin \geq 8 g/dL • Bilirubin \leq 2 x ULN • AST/ALT \leq 2 x ULN • Creatinine \leq 1.5 x ULN 
Patients must not have had prior cancer therapy (including biologic, cytotoxic, and experimental therapies and nitrosoureas) within 21 days of registration.

Treatment Plan	Once registered, eligible patients will receive intravenous NU-0129 nominal dose \sim 0.04mg/kg (based on dosing chart) one time. Patients will be monitored with telemetry, vital signs, and labs before, during and after the infusion as indicated in section 5.0. Treatment will be followed by a tumor resection 8-48 hours later. The tissue will be collected and analyzed for bio-distribution and exploratory studies.

NU Study Number: NU 16C01

Statistical Methodology	All patients properly included in the study who undergo surgery for tumor removed will be included in the analysis. Thus, an incorrect treatment schedule or drug administration would result in exclusion from the analysis of the tumor accumulation study. All conclusions will be based on all eligible patients. Sub-analyses may then be performed on the basis of a subset of patients, excluding those for whom major protocol deviations have been identified. However, these sub-analyses may not serve as the basis for drawing conclusions concerning treatment efficacy, and the reasons for excluding patients from the analysis should be clearly reported.
--------------------------------	--

1.0 INTRODUCTION – BACKGROUND & RATIONALE

1.1 Disease Background

Glioblastoma (GBM) is a neurologically debilitating disease, which culminates in death 16-18 months after diagnosis. An incomplete understanding of genetic aberrations leading to tumor growth, invasion and anti-apoptosis, mechanisms of resistance, combined with the lack of effective drugs have conspired to make GBM an incurable disease. In addition to issues noted, drug delivery has long been an issue in treating brain tumors that is not an issue for most other solid tumors.

Glioblastoma (GBM) is a highly malignant brain tumor of astrocytic origin which accounts for over 50% of all gliomas. GBM has an annual incidence rate of 3 to 4 cases per 100,000 people resulting in 240,000 newly diagnosed cases worldwide each year [1,2]; .

The current standard treatment for GBM is surgical resection followed by radiotherapy with concurrent and adjuvant temozolomide (TMZ). For newly diagnosed GBM, the addition of TMZ to surgery and radiation therapy prolongs median survival (from 12.1 to 14.6 months) and increases the five-year survival rate (from 2% to 10%; hazard ratio 0.63; 95% CI 0.53-0.75; p<0.0001) [3].

Bevacizumab, a monoclonal antibody against vascular endothelial growth factor (VEGF), was approved in the US for the treatment of recurrent GBM based on a clinically meaningful and durable objective tumor response rate (ORR 28%-38%, median duration of response 4.2 months). The 6-month-PFS rate in the multiple studies ranged from approximately 29% to 50% and represented a significant improvement over the historical 10-20% 6-month-PFS rate. Despite the improvement in response provided by bevacizumab, most patients with GBM experience relapse within months [4,5] and options for salvage remain extremely limited.

Genetically, GBM is characterized by complex chromosomal abnormalities and extensive intratumor cytogenetic and histological heterogeneity displaying the genetic alterations that govern the processes of cellular proliferation, survival, invasion and angiogenesis [6,7,8]. Common mutations found in GBM include: EGFR overexpression (70%) [9]; TP53, RB, INK4a, PDGF-R, VEGF-R, C- Met and HGF and PTEN [10].

Besides GBM, which features the highest grade of malignancy among glioma (grade IV), lower grade glioma which include grade II and grade III are a heterogeneous group of tumors in which specific molecular features are associated with divergent clinical outcome.

Currently approved therapy for a newly diagnosed GBM patient in the United States includes maximal surgical resection followed by radiation and temozolomide [11]. Upon recurrence there are few approved options and these include surgical implantation of chemotherapy bearing wafers[12] (polifeprosan 20 with carmustine implant, Gliadel® Wafer) and systemic administration of the anti-angiogenic agent bevacizumab, which has shown a partial response rate of 20% in one trial, and 26% in another [13, 14]. Each of these therapies has shown modest improvement in survival of recurrent GBM patients, with notable treatment related toxicities including wound breakdown after surgical resection [15].

1.2 Intervention Background & Overview

NU-0129 is an investigational spherical nucleic acid (SNA) designed to target the silencing of Bcl2L12 gene expression, an overexpressed protein that plays an important role in driving the pathogenesis of glioblastoma multiforme (GBM) and mediating therapeutic resistance [16]. SNAs are three dimensional conjugates consisting of densely functionalized and highly oriented nucleic acids covalently attached to the surface of nanoparticles [17]. NU-0129 is composed of 13nm gold nanoparticles surrounded by siRNAs tailored to recognize Bcl2L12 sequence. Gene silencing using siRNAs conjugated

to these SNAs represents a promising new approach for systemic RNA interference (RNAi)-based therapy of this aggressive malignant brain tumor in humans. This nanoconjugate is one of the first to report stable and robust RNAi delivery to intracranial tumors in rodent GBM models, as they have the capacity to cross both intact and tumor-compromised blood brain barrier (BBB), and has helped develop SNAs as a platform for biotherapeutic gene silencing. Non-human primate and non-primate toxicology studies were completed with NU-0129, with no significant clinical observations.

The impact of NU-0129 on tumor progression in xenogeneic grafts in mice show intravenous administration of NU-0129 at a total injection of 7 mg/kg of the active pharmaceutical ingredient (API) resulted in intraglioma protein down-regulation and impaired tumorigenicity as measured by decreased tumor weight and prolonged survival of xenogeneic mice. Increased intratumoral apoptosis was evidenced by enhanced levels of DNA strand breaks as assessed by Terminal deoxynucleotidyl transferase dUTP nick end labeling (TUNEL) and active caspase-3 staining. Thus, blood-brain barrier/blood-tumor barrier (BBB/BTB) penetration and intra-glioma dissemination of NU-0129 upon systemic administration resulted in increased survival of glioma-bearing animals.

1.2.1 **Pre-clinical Pharmacokinetic studies**

Summary of finding from 126501 AD TK report Text

NU-0129, in the vehicle (phosphate-buffered saline, pH 7.4), was administered by IV bolus once to 3 groups of male and female Cynomolgus monkeys. A concurrent control group received the vehicle on the same regimen. Table T1 presents the study group assignment for the Toxicokinetic portion of the study.

Table T1. ! Study Group Assignment for the Toxicokinetic Portion of the Study

Group Number	Test Article	Dose Level	Dose Volume	Number of Animals	
		(mg/kg)	(mL/kg)	Males	Females
1	Vehicle	0	5	5	5
2	NU-0129	1	5	5	5
3	NU-0129	4	5	5	5
4	NU-0129	8	5	5	5

*The dose levels correspond to the amount of siRNA, the actual test article component, in the neat powdered material.

On the day of dosing, blood samples were collected from all animals prior to dosing and at approximately 3, 10, and 30 minutes, and 2, 8, and 24 hours post-dose. Plasma was analyzed for the concentration of NU-0129 using liquid chromatography with FLD. The results of these analyses were used for toxicokinetic analysis.

The toxicokinetic parameters for NU-0129 in plasma are summarized in Table T2.

Table T2. Toxicokinetic Parameters for NU-0129 in Male and Female Monkeys

Dosage (mg/kg)	Males						Females					
	1		4		8		1		4		8	
	Mean	SD	Mean	SD	Mean	SD	Mean	SD	Mean	SD	Mean	SD
AUC _{last} (µg*h/mL)	0.232 ^{†1}	NA	2.37	1.04	9.82	2.82	0.321 ^{†3}	0.10	3.62	0.71	14.2	1.90
C ₀ (µg/mL)	1.67	0.879	34.0	19.8	131	51.4	3.90	2.31	68.9	18.1	174	36.3
T _{1/2} (h)	NC	NA	0.06	0.00	0.08	0.04	0.05 ^{†3}	0.00	0.05	0.00	0.07	0.01
Cl (mL/h/kg)	NC	NA	1980	863	863	224	3340 ^{†3}	1070	1140	250	570	93.2
V _{ss} (mL/kg)	NC	NA	158	86.7	72.6	26.0	213 ^{†3}	75.3	66.1	22.4	50.2	7.52

N = 5, except where designated with [†]N

Following a single IV bolus dose of NU-0129 to male and female monkeys, exposure increased with increasing dose. The increase in AUC_{last} was greater than dose proportional as NU-0129 dose increased from 1 mg/kg to 8 mg/kg. NU-0129 exposure, in terms of AUC_{last}, was slightly higher in females than in males, but differences were <2-fold.

Clearance, V_{ss}, and terminal half-life were not calculable at 1 mg/kg for males. Mean Clearance, ranging from approximately 600 to 3000 mL/h/kg, was moderate to high (approximately 20% to 120% of hepatic blood flow in the monkey as reported by Davies and Morris, 1993) and decreased as dose increased. Mean V_{ss} was small, ranging from approximately 50 to 200 mL/kg (approximately 10% to 30% of total body water in the monkey as reported by Davies and Morris, 1993) and also decreased with increasing dose. This resulted in a short terminal elimination halflife that ranged from approximately 2 to 9 minutes for individual animals. Clearance- and V_{ss} values were approximately 1.4- to 2-fold higher for males than females, but half-life values were similar.

1.2.2 **Pre-clinical toxicity studies**

The non-clinical toxicity studies for Bcl2I12-2-SNA in cynomolgus monkeys and rats showed no significant test article-related clinical observations. Purple and/or blue discoloration of various body surfaces (facial area, oral cavity, limbs and/or trunk) were noted in medium and high dose groups, along with macroscopic observations of blue discolorations in some tissues of high dose group. Consistently, microscopic findings indicated black pigment within macrophages and endothelium in corresponding tissues, i.e., adrenals, liver, lymph nodes, and spleen. These pigments are likely attributed to the gold-nanoparticles. Importantly, toxicity was not observed at the cellular or tissue level in the presence of the gold-nanoparticles.

Administration of Bcl2I12-2-SNA to male and female cynomolgus monkeys was well tolerated with all animals surviving to the scheduled primary (Day 2 post-dose) or recovery (Day 14 post-dose) necropsies. Significantly, there were no clinical observations in hematology, coagulation, serum chemistry, or urinalysis parameters, or organ weight. Blue discoloration was noted in many of the tissues of the monkeys, more so at the higher dose levels, and this was correlated to the

presence of pigment within macrophages and endothelium in the various tissues. The pigment appeared black by light microscopy and is likely attributed to the gold-nanoparticles. There did not appear to be any cellular or tissue level toxicity to the presence of the gold-nanoparticles. Bcl2I12-2-SNA appears to be a promising, clinically-viable drug product. There is no significant toxicity associated with the chemistry or manufacturing of the drug product. All pre-clinical studies were performed under conditions of Good Laboratory Practice (GLP).

1.2.3 More in-depth results and summary.

The dose levels tested were 1mg/kg (low), 4mg/kg (medium) and 8mg/kg (high) via intravenous (bolus) injection to male and female cynomolgus monkeys. The dose levels correspond to the amount of siRNA, the actual test article component, in the neat powered material. There was 0.025 grams of siRNA per 1.00 gram of the neat, powered material.

All toxicology and cardiovascular animals survived to the end of the study. There were no test article-related effects on body weights, hematology, coagulation, serum chemistry, urinalysis, or organ weights. In addition, administration of a single dose of NU-0129 at high dose (8 mg/kg) via intravenous (bolus) injection to male and female cynomolgus monkeys resulted in moderately decreased blood pressure (systolic, diastolic, and mean blood pressure); this effect was only detected in the test article formulation group and not the control group. NU-0129 at 8 mg/kg had no effect on heart rate, pulse pressure, body temperature, ECG intervals (PR, QRS, RR, QT, or QTcB), or ECG waveform morphology.

Test article-related clinical observations of purple and/or blue discoloration of various body surfaces (facial area, gums, forelimb[s], hindlimb[s], oral cavity, and/or trunk [dorsal and ventral]) were noted in the 4 and 8 mg/kg toxicology group males and females and in the 8 mg/kg cardiovascular group males and females throughout the study, and in a single 1 mg/kg toxicology group male on study days 4 and 5. In general, purple discoloration was noted only on the day of dose administration and blue discoloration was noted for the remainder of the recovery period.

Test article-related macroscopic observations of blue discoloration were noted in many tissues (adrenals, gastrointestinal tissues [esophagus, stomach, duodenum, jejunum, ileum, cecum, colon, and rectum], epididymis, lymphoid tissues [spleen, lymph nodes, and thymus], skin, liver, tongue, urogenital tissues [seminal vesicles, testes, vagina, and urinary bladder]) of most males and females at 8 mg/kg on study days 2 and 14. Blue discoloration of the liver, spleen, lymph nodes, skin, tongue, and scattered other tissues was also noted in the 4 mg/kg/day group males and females on study days 2 and 14. In the 1 mg/kg/day group males and/or females, blue discoloration was noted only in the liver, adrenals, epididymis, testes, and spleen. In addition, blue discoloration of the bone was noted in the 4 and 8 mg/kg group males and females on study day 14. Procedurerelated- macroscopic findings of dark red area(s) at the injection site were noted in all animals, including the control group, on study days 2 and 14.

Test article-related microscopic findings of pigment in the adrenals, bone marrow (femur and sternum), Kupffer cells in the liver, lymph nodes (axillary, mandibular, and/or mesenteric), and spleen were noted in all test article-treated male and female groups on study day 2 and in all test article-treated male groups as well as 4 mg/kg and 8 mg/kg group females on study day 14. In addition, pigment was noted in the skin and tongue in the 4 and 8 mg/kg group males and females on

study days 2 and 14. Injection site findings of acute perivascular hemorrhage were noted in all groups, including the control group on study days 2 and 14. -Procedurerelated- injection site findings of perivascular acute inflammation (neutrophils, edema, and fibrin exudation) was noted at all dose levels on study day 2, and subacute inflammation was noted in the 4 and 8 mg/kg group males on study day 14.

Since the neat test article is comprised of spherical nucleic acids in the presence of gold nanoparticles and the dosing formulation was described as being an opaque dark red liquid, it is hypothesized that it is the gold nanoparticles that are responsible for the blue discoloration of the tissues.

Based on the results of this study, a single intravenous (bolus) injection of NU-0129 to cynomolgus monkeys resulted in a no-observed-adverse-effect level (NOAEL) of 8 mg/kg for both systemic and local assessments.

1.3 Rationale for the Current Study

NU-0129 has undergone extensive pre-clinical testing and appears to be a viable, safe, and potentially efficacious drug product in GBM. The NOAEL determined for non-human primates is 8mg/kg (nucleic acid dose concentration). One fiftieth of the human equivalent dose (HED) is around 0.04 mg/kg. Being that this is a Phase 0 first in human trial, micro-dosing will be utilized with a target dose of 0.04 mg/kg.

NU-0129 is an ideal potential agent for the treatment of GBM for its ability to cross the blood brain barrier giving it potential bioavailability within the tumor bed. Additionally, targeting the tumorigenic Bcl-2 could promote apoptosis and tumor kill for patients treated with NU-0129. Given the preclinical data as well as data from animal studies in rats, mice and non-human primates, it has been shown that NU-0129 successfully crosses the blood brain barrier, successfully induces apoptosis and in the mouse model leads to improved survival in animal models with GBM.

1.4 Exploratory Studies

An exploratory objective will be to assess the level of Bcl2L12 expression in the primary tumor. Expression of Bcl2L12 is upregulated in most GBM patients as higher expression results in resistance to apoptosis. A survival analysis in 343 GBM patients with different levels of Bcl2L12 demonstrated a decreased survival rate correlating with increased expression of Bcl2L12.

2.0 OBJECTIVES & ENDPOINTS

2.1 Primary Objective & Endpoint

- The primary objective is to assess the safety of intravenous NU-0129 in patients with recurrent GBM or GS.
- The total incidence of adverse events will be evaluated using CTCAE v4.03 from the time of informed consent to 21 days after study drug administration. Adverse events will be monitored during and immediately after the infusion as well as weekly for 21 days after treatment administration.

2.2 Secondary Objectives & Endpoints

2.2.1 Pharmacokinetics

- To analyze drug concentration in serum at specific time points after drug administration.
- PK blood samples will be collected post-infusion at 1, 3, 5, 10, 30, and 60 minutes, and 4, 8, and 24 hours post infusion.

2.2.2 Bio-distribution

- To demonstrate intratumoral penetration of NU-0129
- Tissue will be collected during the scheduled surgery and analyzed using ICP-MS

2.2.3 Feasibility

- To assess the feasibility of giving NU-0129 as a standard treatment for recurrent GBM or GS.
- Feasibility will be calculated as the rate of successful production, delivery, and administration of the investigational product and subsequent resection.

2.3 Exploratory Objectives & Endpoints

2.3.1 Bcl2L12 expression levels

To analyze tumor tissue for Bcl2L12 expression levels after NU-0129 administration.

Tissue collected during surgery will be analyzed using RNA analysis techniques. A comparison will be drawn with archival tissue collected at screening for any patients where it is available.

2.3.2 Preliminary response (PFS and OS at 6 months; ORR)

Preliminary response will be measured as an exploratory outcome. Progression Free Survival (PFS) and Overall Survival (OS) will be measured at 6 months after treatment.

Overall Response Rate will also be measured by brain MRI at least every 12 weeks after treatment using RANO criteria

3.0 PATIENT ELIGIBILITY

The target population for this study is patients with recurrent glioblastoma multiforme or gliosarcoma. This will be a single-center trial conducted at Northwestern Medicine.

A total of 6-8 subjects will be needed for this trial. Approximately 8 potentially eligible patients are seen per month, and it is anticipated that at least 1 per month will be accrued. Potential patients may be referred to the Principal Investigator (PI) at Northwestern University, [name], at [contact].

Eligibility will be evaluated by the study team according to the following criteria. Eligibility waivers are not permitted. Subjects must meet all of the inclusion and none of the exclusion criteria to be registered to the study. Study treatment may not begin until a subject is registered. Please refer to Section 11 for complete instructions regarding registration procedures.

3.1 Inclusion Criteria

3.1.1 Patients must have histologically proven glioblastoma multiforme (GBM) or Gliosarcoma (GS).

3.1.2 Patients must have measurable disease by RANO 2010 criteria at the time of registration (pre-operative).

3.1.3 Patients must have failed at least one regimen of chemo or radiation therapy.
NOTE: There is no limit to the number or types of prior therapy.

3.1.4 The patient must be a candidate for surgical debulking (either subtotal or gross total resection). Biopsy-only candidates will not be eligible.

3.1.5 All patients must be capable to voluntarily sign an informed consent indicating that they are aware of the investigational nature of this study prior to registration.

- 3.1.6 Patients must be \geq 18 years old.
- 3.1.7 Patients must have a Karnofsky performance status of \geq 70.
- 3.1.8 Patients must have adequate bone marrow, liver, coagulation and renal function within 7days prior to study registration, as defined below:
 - WBC \geq 3,000/ μ L
 - ANC \geq 1,500/mm 3
 - Platelet count of \geq 100,000/mm 3 (*Note: Transfusion or growth factor may be used for eligibility outside of 7 days*)
 - Hemoglobin \geq 8 g/dL (*Note: Transfusion may be used for eligibility outside of 7 days*)
 - Bilirubin \leq 2 x ULN
 - AST/ALT \leq 2 x ULN
 - Creatinine \leq 1.5 x ULN
 - Urine protein \leq 30 mg/dL
 - Cholesterol \leq 300 mg/dL
 - INR \leq 1.5 x ULN
 - PT/PTT \leq 1.5 x ULN
- 3.1.9 Any patient who has had a recent surgery should have recovered from all effects of the surgery and be cleared by their surgeon.
- 3.1.10 Females of child-bearing potential (FOCBP) and males must agree to use adequate contraception (e.g. hormonal or barrier method of birth control; abstinence) prior to study entry, for the duration of study participation, and for 21 days following completion of therapy. Should a female patient, or a male patient's partner, become pregnant or suspect she is pregnant while participating in this study, the patient should inform her or his treating physician immediately.

NOTE: A FOCBP is any woman (regardless of sexual orientation, having undergone a tubal ligation, or remaining celibate by choice) who meets the following criteria:
 - Has not undergone a hysterectomy or bilateral oophorectomy
 - Has had menses at any time in the preceding 12 consecutive months (and therefore has not been naturally postmenopausal for > 12 months)
- 3.1.11 FOCBP must have a negative pregnancy test (either urine or serum) within 14 days prior to registration.

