3.2 Exclusion Criteria

- 3.2.1 Patients must not have any significant infections or medical illnesses that in the investigator's opinion cannot be adequately controlled with appropriate therapy or would compromise the patient's ability to tolerate NU-0129.
- 3.2.2 Patients must not have a history of any other cancer unless they are in complete remission and off of all therapy for that disease for a minimum of 3 years.

NOTE: Non-melanoma skin cancer or carcinoma in-situ of the cervix are exceptions and may be permitted after discussion with study QAM.

- 3.2.3 Patients must not have had radiation therapy \leq 12 weeks prior to starting study treatment.

3.2.4 Patients must not have had prior cancer therapy (including biologic, cytotoxic, and experimental therapies, nitrosoureas, and Gliadel wafers or other surgically implantable antitumor treatment) within 21 days of registration. If questions arise, please contact the PI.

NOTE: Patients must not have had Novocure within 24 hours of registration

3.2.5 Hormonal tumor therapies should not be administered within 14 days of registration. Exceptions may be discussed with the PI.

3.2.6 Patients must not have symptomatic hypertension.

3.2.7 Patients with known human immunodeficiency virus (HIV) infection or chronic or acute Hepatitis B or C are not eligible.
Note: Patients do not need to have HIV, Hepatitis B, or Hepatitis C testing at screening.

3.2.8 Female patients who are pregnant or breast feeding are not eligible.

3.2.9 Patients are not eligible if they are unwilling or unable to comply with the protocol.

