4.6 Duration of Therapy

Within 14 days of study registration, patients will receive intravenous NU-0129 one time at nominal dose 0.04mg/kg. Patients will be admitted the morning of the planned NU-0129 infusion, and a tumor resection will occur 8-48 hours after administration. Patients will remain inpatient for standard of care post-operative procedures, including an MRI of the brain. Discharge will take place when clinically appropriate.

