4.9 Patient Replacement

If a patient withdraws for any reason after consent or registration but before receiving investigational product, he or she may be replaced.

If a patient receives study drug and does not have a post-treatment surgical resection, or the surgery is delayed beyond 48 hours of treatment for any reason, the patient will be evaluable for toxicity, but will be inevaluable for all other study endpoints; another patient may be added to accrual.

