5.0 STUDY PROCEDURES

Table 5.1 – On-Study Procedures (**see table 5.2 for follow-up procedures)

Time Period	Screening ¹	Inpatient		
		Treatment Administration	Surgery	Post-op ¹²
Informed Consent ¹	X			
Medical history	X			
Physical exam ²	X			X
Karnofsky PS	X			X
Vitals	X	X ³	X	
Toxicity assessment	X	X		X ¹³
Conmeds	X	X		X
MRI ⁴	X			X
CBC with diff ⁵	X	X ⁵		X
Chemistry panel ⁵	X			X
Phosphorus + Mg ⁵	X	X		X
PT/PTT/INR ⁵	X			X
Cholesterol panel ⁵	X			X
Urinalysis	X			
Pregnancy test ⁶	X			
ECG	X			X ⁷
NU-0129 Infusion ⁸		X		
Tumor Resection			X ¹¹	
PK blood samples		X ⁹		
Tissue collection	X ¹⁰			X ¹¹

¹ All screening procedures must be completed within 14 days of registration unless otherwise noted (Labs and pregnancy test must be within 14 days of registration). Informed consent can be within 28 days prior to registration.

² Includes complete neurologic exam and weight. Height will be recorded at screening.

³ Vital signs should include pulse and blood pressure. On the day of treatment administration, vitals will be measured using continuous telemetry immediately prior to, during, and for at least 8 hours post infusion. Vital signs will then be measured at least every 4 hours for a total of 24 hours post-infusion. Vital signs will also be assessed continuously throughout the patient's surgical resection.

⁴ A brain MRI with and without contrast will be performed at baseline (within 21 days of registration) and after surgery as part of standard of care post-op procedures, likely within 48 hours of surgical resection.

⁵ Laboratory tests (including, CBC, Chemistry, PT/PTT/INR, Phosphorus, Mg, and Cholesterol panel) must be drawn within 7 days of registration and treatment. If treatment occurs more than 7 days after the indicated labs, they should be repeated. CBC w/ differential should include WBC, ANC, ALC, and Platelets. A complete chemistry panel will be drawn including Sodium, Potassium, Chloride, Bicarbonate, BUN/Creatinine, AST, ALT, Total Bilirubin, Calcium, and Albumin. CBC with diff will be repeated pre-dose on the day of study treatment.

⁶ A pregnancy test will be performed for females of child-bearing potential at screening (serum or urine) within 14 days of registration.

⁷ An ECG will be performed at screening and only as needed for standard of care toxicity management during post-operative observation.

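### The only scheduled pregnancy test is tied to registration and can be 28 days old at the NU-0129 infusion, while the listed safety blood tests must be within 7 days of treatment or repeated

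*Combined protocol and SAP*

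**What the plan says.** Eligibility section 3.1.11 reads: "FOCBP must have a negative pregnancy test (either urine or serum) within 14 days prior to registration". Table 5.1 footnote 6 repeats the same anchor: "A pregnancy test will be performed for females of child-bearing potential at screening (serum or urine) within 14 days of registration". Footnote 1 gives the same 14-day window. The pregnancy test row of Table 5.1 is marked in the Screening column only, and Table 5.2 has no such row.

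Dosing may come later. Section 4.6 says: "Within 14 days of study registration, patients will receive intravenous NU-0129 one time". Section 3.0 fixes the order of events: "Study treatment may not begin until a subject is registered".

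Other laboratory tests are handled differently. Footnote 5 of Table 5.1 covers CBC, chemistry, PT/PTT/INR, phosphorus, magnesium and cholesterol. It ties them to both registration and treatment with a 7-day limit, and adds: "If treatment occurs more than 7 days after the indicated labs, they should be repeated". It also says: "CBC with diff will be repeated pre-dose on the day of study treatment". The pregnancy test is not in its list.

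The exclusion itself, section 3.2.8, is plain: "Female patients who are pregnant or breast feeding are not eligible". Section 3.1.10 requires contraception from before study entry until 21 days after therapy, and prompt reporting of a suspected pregnancy.

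**The concern.** The exclusion protects against exposure, and exposure happens at the infusion, not at registration. The protocol accepts for most blood tests that a result can go stale between the two dates. It does not apply that reasoning to pregnancy status, which can change in the interval and which a simple test can check.

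The stakes are those of a first-in-human agent. Section 8.1.10 says that side effects in this population are not fully known, and the toxicology summary in sections 1.2.2 and 1.2.3 describes no reproductive or developmental study. In the monkey study, pigment was still present in tissues on day 14 and discoloration included reproductive organs. The doses there were 1 to 8 mg/kg, which is 25 to 200 times the nominal 0.04 mg/kg (1/0.04 and 8/0.04), so this is not evidence of fetal harm. It does mean that the short plasma half-life in monkeys is not full reassurance. Section 4.2 expects no response from this dose, so no anticipated benefit to the patient offsets an avoidable exposure. One infusion cannot be taken back, so the last useful check is the one before it.

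**Working it through.** The protocol states no interval from pregnancy test to infusion, so there is no figure of its own to reproduce. The maximum follows from adding the scheduling windows.

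**Inputs from the protocol**
- Test to registration: 0 to 14 days (3.1.11; Table 5.1 footnotes 1 and 6).
- Registration to infusion: 0 to 14 days (4.6).
- Registration must come before treatment (3.0), so the two windows add.
- Blood tests listed in footnote 5: at most 7 days before treatment, otherwise repeated.
- CBC: repeated before dosing on the treatment day (footnote 5).

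Footnote 1 mentions 14 days for laboratory tests as well. It applies only where nothing else is noted, so footnote 5 governs those tests.

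**Maximum age of the result at infusion**

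Maximum age = (maximum test to registration) + (maximum registration to infusion)

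- Pregnancy test: 14 + 14 = 28 days.
- Footnote 5 blood tests: 7 days.
- CBC: 0 days.

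The excess over the footnote 5 limit is 28 - 7 = 21 days.

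**How far along an undetected pregnancy could be at infusion**

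This step needs a detection lag, which the documents do not give. I assume that a test turns positive 7 to 14 days after conception.

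Maximum days from conception = maximum test age + detection lag

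| Rule | Maximum test age (days) | Lag 7 days | Lag 14 days |
|---|---|---|---|
| As written | 28 | 28 + 7 = 35 | 28 + 14 = 42 |
| Within 7 days of treatment | 7 | 7 + 7 = 14 | 7 + 14 = 21 |
| Treatment day | 0 | 0 + 7 = 7 | 0 + 14 = 14 |

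These are upper limits, with both protocol windows fully used. A treatment-day test shortens the blind period to the detection lag. It does not remove it.

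**The case against.** The strongest counter-argument is that the residual risk is low and partly controlled. There are 6-8 patients and one dose, described in section 1.3 as about one fiftieth of the human equivalent dose. Contraception, a negative screening test and a duty to report a suspected pregnancy are all in place. This stands, and it limits how much weight the point deserves. But contraception and reporting depend on adherence and on the patient suspecting pregnancy, and neither triggers a test before the infusion.

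The contrast with footnote 5 can also be called selective. Urinalysis is scheduled at screening only, and the ECG is repeated only if clinically needed, so pregnancy is not the sole test left at screening. The amendment log explains the pre-dose CBC as a way to judge whether changes are due to the drug, not as an eligibility re-check. Both observations are correct. The case therefore rests on the 7-day repeat rule and on the purpose of the exclusion, not on the CBC; the CBC matters only as a convenient occasion for the test.

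The 35-42 day figure depends on an assumed lag and on both windows being at their limits. That is also correct, but the 28 days needs no such assumption.

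Finally, institutional pre-operative practice might include a pregnancy test. The protocol does not say so. Resection follows the infusion by 8-48 hours, so a test tied to surgery could come after exposure.

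**Conclusion.** The concern holds. As written, a pregnancy test can be 28 days old at the infusion, against 7 days for the blood tests in footnote 5, and no provision requires a repeat. The 28 days comes from the protocol's own windows; the 35-42 days from conception rests on the assumed 7-14 day detection lag. The judgement that the absolute probability is small rests on a further assumption, that few of the 6-8 patients will be of child-bearing potential, because the documents give no age or sex distribution. This is a participant-safety gap in the schedule. It does not touch the sample size, any endpoint or any analysis. It should be corrected because the remedy is easy and the exposure cannot be reversed.

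**What to change.** For women of child-bearing potential:

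- Keep the registration test and add a negative urine or serum pregnancy test on the treatment day, taken with the pre-dose CBC and with the result available before the infusion starts.
- As a minimum alternative, add the pregnancy test to footnote 5, so that it must be within 7 days of treatment or be repeated.
- Mark the test in the Treatment Administration column of Table 5.1, amend 3.1.11 and footnote 6 to match, and state that a positive result means no infusion.
- Optionally, name this case in section 4.9. That section already lets a patient who withdraws for any reason "after consent or registration but before receiving investigational product, he or she may be replaced", so this would be a clarification, and the main change does not depend on it.

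The cost is a short amendment and at most one extra urine test per woman of child-bearing potential, or a serum test added to a draw already planned. Patients are admitted that morning under section 4.6. The infusion may wait briefly for the result, and a positive or indeterminate result would delay or cancel both the infusion and the linked resection slot.
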